### I Research Background

Alzheimer's disease, a common degenerative disease of the central nervous system, refers to the overall impairment of intelligence, memory and personality that occurs in old age (age  $\geq 60$  years), manifested by memory, calculation, thinking, language, orientation and emotional disorders, as well as personality changes, and a decline in the ability to engage in social activities and the ability to live on one's own. The number of dementia patients in China accounts for about a quarter of the global population, making it the country with the largest number of dementia patients in the world. Studies have found that type 2 diabetes is highly susceptible to the development of dementia due to hyperglycemia and insulin resistance, and the risk of vascular dementia in diabetic patients is 2.27 times higher than that in non-diabetic patients. Alzheimer's patients with comorbid diabetes are at high risk for physical and mental health risks due to cognitive impairment and mental and behavioral abnormalities, and are almost incapable of self-care, and are heavily dependent on their caregivers. Caregivers are faced with complex clinical symptoms such as diabetic foot and neuropsychiatric manifestations of dementia, and may even develop a sense of despair

and fear. The provision of holistic, continuous, professional and personalized care services for caregivers is an urgent issue that needs to be addressed.

## **II Purpose of Research**

This project aims to build a mobile health supportive care program for family caregivers with dementia combined with diabetes, and to evaluate the clinical application effect of the mobile health supportive care program for family caregivers with dementia combined with diabetes. The research results will provide more economical and efficient care guidance for family caregivers, thus improving the overall quality of care and quality of life for patients with dementia and diabetes.

## **III Research Method**

### **(1) Object of Study**

#### **1) Source of the study subjects and the sampling methods**

The convenience sampling method started from May 2022 to the end of the sample number, and family caregivers with dementia and diabetes in 5 community neighborhood committees (cities) and 10 villages (rural areas) of a community health service center that met the inclusion criteria were selected.

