### **4) Sample size estimation**

The sample size is calculated according to the ratio of 1:1 between the test group and the control group, and the sample size calculation method of "difference test of two sample means comparison" is used.

The calculation formula is:

$$n_1=n_2=2\left[\frac{(\mu_{\alpha}+\mu_{\beta})}{\delta/\sigma}\right]^2 + \frac{1}{4}\mu^2$$

Based on the literature review, with the caregiver care burden as the main outcome measure of this study,  $n_1$  and  $n_2$  were the required sample size, respectively;  $\alpha = 0.05$ ,  $\beta = 0.1$ , two-sided test,  $\mu_0.05/2=1.96$ ,  $\mu_0.1=0.282$ , mean difference  $\delta = 33.91-27.04=6.87$ , and overall standard deviation of the intervention  $\sigma = 6.85$ . After calculation, the sample size of both groups was 22 cases, considering 15% shedding

rate, at least 26 cases in each group, a total of 52 cases. Finally, 30 patients were included in each group, totaling 60 patients.

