### **(3) Data Processing and Statistical Analysis**

Statistical data was analyzed using SPSS 25.0 software. Quantitative data were represented by normal distribution ( $\pm s$ ), non-normal by M (QR); qualitative data by n (%). Quantitative data is designed to compare two independent samples. If sample data follows normality, independent sample t-test is used, otherwise Mann Whitney U test is used; for comparison before and after intervention; if the difference follows normal distribution, paired t-test is used, otherwise Wilcoxon rank sum test is used. To compare qualitative data between different groups, use  $\chi^2$  test or Fisher's exact test; compare rank data between different groups. Subject analysis (Per-protocol Subjects Analysis, PP).

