## **四、The Project Involves the Implementation Plan of the Ethical Part**

- Study subjects, number of cases, intervention methods, enrollment criteria, and exclusion criteria

There were 60 elderly family caregivers with dementia and diabetes, and the intervention method was mobile medical supportive care program. The enrollment criteria were: ① Care nannies and hourly workers with legal kinship (such as spouse, children or siblings), etc.; ② worked for 8 hours / day and 5 days / week for 1 month; ③ well-aware

and reading and understanding adults; ④ has at least a smart phone (Internet access) and skilled use; ⑤ informed consent and voluntary participation in research. Exclusion criteria: ① Severe physical or mental illness; ② patients with drug or alcohol dependence; ③ caregivers are participating in similar intervention studies.

- Specimens to be collected and the sources of the specimens

No specimens were collected

- Recruitment and protection measures of the subjects

① Recruitment: Select family caregivers of elderly people with dementia and diabetes in 5 community neighborhood committees (cities) and 10 natural villages (rural areas) in the jurisdiction of a community health service center that meet the exclusion criteria.

② Protection: Carers have the right to refuse to answer any items that cause psychological discomfort and provide door-to-door assessment services whenever possible.

- Research risks and preventive measures

No medication or any radioactivity, invasive procedures, and in principle will not cause any risk or adverse effects on the physical health of the subject.

- The benefit of the study

Participation in this study may help subjects to better understand the health of their caregivers, and the intervention is expected to improve their social support function and reduce their care burden and poor mood. However, it is also possible that participation in this study did not directly benefit the subjects.

- Exps and compensation for subjects' participation in the project

Throughout the study, the subjects were unpaid and no fees were charged to the subjects. When the subject is injured by his participation in this study, the necessary medical measures will be taken for treatment and compensation will be paid in accordance with the current national laws. If in this study, lost work or transportation expenses, reasonable expenses will be compensated.

- Information and confidentiality about the subjects

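### The plan does not say how, or at what unit, carers enter the two groups, and its primary comparison uses neither baseline burden nor urban/rural setting

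*Combined protocol and SAP*

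**What the plan says.** All references are to the combined protocol and SAP.

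- **Source of subjects, section III (1) 1).** The text reads "The convenience sampling method started from May 2022 to the end of the sample number", and the carers come from "5 community neighborhood committees (cities) and 10 villages (rural areas) of a community health service center". That is 15 communities in two settings under one health centre. The recruitment item in the ethics part repeats the same source and does not mention groups.
- **Sample size, section III (1) 4).** The number is worked out "according to the ratio of 1:1 between the test group and the control group", "with the caregiver care burden as the main outcome measure of this study". This is the only text on the two groups. It gives a ratio and no procedure.
- **Analysis, section III (3).** "Quantitative data is designed to compare two independent samples": an independent-samples t-test under normality, otherwise Mann-Whitney U. Before-and-after change is tested by a paired t-test or Wilcoxon test. No covariate, stratum or community term appears.

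The section on research tools lists the Caregiver Burden Inventory (CBI). Since the analysis compares values before and after the intervention, I take it that CBI is measured at baseline.

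**The concern.** The stated purpose is to evaluate the effect of a care programme, which is a causal question. Whether an unadjusted difference in CBI answers it depends on how the groups are formed, and the plan leaves that open. As written, it would permit individual randomisation, a recruiter's choice, assignment of whole communities, or one arm in the city and the other in the villages. These differ greatly in what the t-test can show.

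Urban and rural carers may differ in burden for reasons unrelated to the programme. If the urban share differs between arms, that difference passes into the estimated effect. If whole communities are assigned, carers from one community are not independent, and the individual-level test understates the standard error. Two variables that would help under any of these schemes, baseline CBI and setting, are available and unused.

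**Working it through.** **1. The plan's own figure.** Inputs from section III (1) 4): δ = 6.87, σ = 6.85, two-sided α = 0.05, β = 0.1.

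n = 2[(1.96 + 1.282)/(6.87/6.85)]² + 1.96²/4 = 20.90 + 0.96 = 21.86, so 22 per group. With 15% drop-out, 22/0.85 = 25.9, so 26 per group and 52 in total. Both stated figures reproduce. (The printed 0.282 for the β quantile would give 11 per group. The stated 22 used 1.282, so this is a misprint and a separate matter.) The sample-size arithmetic is not at issue here.

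**2. Individuals randomised.** The t-test is valid. In a simulation of 15 communities of 4 carers, each split two and two, its type I error was 4.8%, 4.4%, 3.8% and 3.1% at assumed intracluster correlations (ICC) of 0.01, 0.05, 0.10 and 0.20. There is no inflation. What is lost is precision: adjusting for a baseline with correlation ρ to follow-up multiplies the error variance by about 1 − ρ². The documents give no ρ.

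**3. Groups unbalanced by setting.** The documents give no urban-rural difference, so this is an assumed range. Bias = (urban-rural difference) × (difference in urban share).

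Example: 0.5 SD × (0.70 − 0.30) = 0.2 SD = 0.2 × 6.85 = 1.37 points, which is 1.37/6.87 = 20% of the planned effect. With 30 per arm the noncentrality is 0.2 × √(30/2) = 0.775, and the two-sided t-test on 58 degrees of freedom rejects with probability 0.119.

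False-positive rate at 30 per arm with no programme effect:

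| Assumed urban-rural difference | Urban share differs by 20 points | 50 points | 100 points |
|---|---|---|---|
| 0.25 SD | 5.4% | 7.6% | 15.9% |
| 0.5 SD | 6.7% | 15.9% | 47.8% |
| 1 SD | 11.9% | 47.8% | 96.8% |

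**4. Whole communities assigned, with no setting effect.** Average size is 60/15 = 4 carers, so the design effect is 1 + 3 × ICC. Simulating 7 against 8 communities gives a t-test type I error of 5.4%, 6.8%, 8.4% and 12.3% at assumed ICCs of 0.01, 0.05, 0.10 and 0.20.

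Precision at ICC 0.10: 30 × 0.85 = 25.5 completers per arm. Dividing by 1.30 gives 19.6 effective. If drop-out shrinks communities to 51/15 = 3.4 carers, the design effect is 1.24 and the effective number is 20.6. Both fall below the stated 22.

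**The case against.** A reader might infer from the convenience sample that allocation is non-random. The documents do not support that. The sentence stands under a heading on source and sampling. It describes how carers enter the study and does not exclude randomising them afterwards. Section III is brief throughout, so its silence shows only that allocation is undescribed.

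If individuals are randomised, the planned test needs no correction. An urban-share difference of 40 points or more would then arise with probability of only about 0.2% to 0.4% (assuming one-third to one-half of carers urban), so the 12% figure belongs to non-random assignment. Nothing in the documents says that whole communities are assigned or that arm follows setting. All communities also belong to one health centre. Clustering is modest at about four carers per community.

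These points stand, and they make the risk of bias conditional. They do not justify leaving method and unit unstated, or leaving out two variables that are already in hand.

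**Conclusion.** The point holds as a gap in the design description joined to an avoidable weakness in the analysis. It does not show that the study is non-randomised, that setting and programme are completely confounded, or that no causal conclusion is possible. A reader might draw those stronger conclusions, but each needs an allocation rule that the plan does not state.

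The size depends on that missing rule. It runs from no bias and some lost precision under individual randomisation, through about 12% false positives in the 70%/30% example, to 47.8% if arms coincided with settings that differ by 0.5 SD. Confounding by setting is the larger risk; clustering matters only if communities are the unit. Every setting difference, imbalance and ICC used here is an assumption.

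The change of analysis is worth making in any case: it adds precision if the groups are randomised and reduces measured confounding if they are not.

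**What to change.** **Section III (3).** Make the primary between-group analysis an ANCOVA of follow-up CBI on group, baseline CBI and urban/rural setting. Report the adjusted difference with its 95% confidence interval.

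**Section III (1).** State how, by whom and at what unit carers are assigned. The preferred wording is individual 1:1 randomisation from a computer-generated list, stratified by urban/rural setting and concealed until consent and baseline assessment are complete.

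**If groups have already been formed another way** (recruitment was to start in May 2022):

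- Formed without randomisation: call the study non-randomised, use the same adjusted model, and limit the conclusion to adjusted association.
- Whole communities assigned: also add a random community effect with small-sample degrees of freedom, and restate the power. At an assumed ICC of 0.10, about 20 effective carers per arm remain after 15% drop-out, against the stated 22. Keeping the stated power would need about 22 × 1.24/0.85 = 32.1 to 22 × 1.30/0.85 = 33.6 recruited per arm, that is 33 to 34 against the planned 30.

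**Cost.** Under individual randomisation: a random list, a concealment step, a few sentences of text and slightly more analysis work, with no extra participants. One limit remains: if programme and setting coincide, no adjustment can separate them.

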#### **2) Inclusion criteria for the study subjects**

Caregivers:

- Carers have legal kinship with the patient (such as spouse, children, or siblings), nannies and hourly workers who do not charge care fees;
- work 8 hours / day and 5 days / week for 1 month;
- aware, reading and understanding adults;
- has at least one smart phone (access to Internet) and skilled use;

- informed consent and voluntary participation in investigation and research.

Care recipients:

- meets the diagnostic criteria for senile dementia;
- meets the diagnostic criteria for type 2 diabetes;
- patients are 60 years old and the resident population in the area.

### **3) Exclusion criteria for the study subjects**

Caregivers:

- severe physical or mental illness;
- people with drug or alcohol dependence;
- caregivers are participating in similar intervention studies.

Care recipients:

- Serious physical illness, major disease or terminal disease;
- patients with drug or alcohol dependence.

### **4) Sample size estimation**

The sample size is calculated according to the ratio of 1:1 between the test group and the control group, and the sample size calculation method of "difference test of two sample means comparison" is used.

The calculation formula is:

$$n_1=n_2=2\left[\frac{(\mu_{\alpha}+\mu_{\beta})}{\delta/\sigma}\right]^2 + \frac{1}{4}\mu^2$$

Based on the literature review, with the caregiver care burden as the main outcome measure of this study,  $n_1$  and  $n_2$  were the required sample size, respectively;  $\alpha = 0.05$ ,  $\beta = 0.1$ , two-sided test,  $\mu_0.05/2=1.96$ ,  $\mu_0.1=0.282$ , mean difference  $\delta = 33.91-27.04=6.87$ , and overall standard deviation of the intervention  $\sigma = 6.85$ . After calculation, the sample size of both groups was 22 cases, considering 15% shedding

rate, at least 26 cases in each group, a total of 52 cases. Finally, 30 patients were included in each group, totaling 60 patients.

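### Does the beta quantile printed as 0.282 mean that the trial was sized at about 61% power rather than 90%?

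*Combined protocol and SAP*

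**What the plan says.** The calculation is in section III (1) 4), Sample size estimation, of the combined protocol and SAP. It compares two means, with numbers set "according to the ratio of 1:1 between the test group and the control group", and takes caregiver burden as the main outcome. The inputs are a "two-sided test" at alpha 0.05, beta 0.1, an alpha quantile of 1.96, a beta quantile printed as 0.282, a mean difference of 33.91 − 27.04 = 6.87 and a standard deviation of 6.85.

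The results follow in three steps. First: "After calculation, the sample size of both groups was 22 cases, considering 15% shedding". Then, allowing for that loss: "at least 26 cases in each group, a total of 52 cases". Last: "Finally, 30 patients were included in each group, totaling 60 patients". The section gives no power for the 30 per group adopted.

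**The concern.** A reader who puts the printed quantiles into the printed formula gets 11 per group, not 22. The printed 0.282 also disagrees with the beta of 0.1 in the same sentence, because it corresponds to about 61% power. This is the only sample-size justification in the document. If the lower quantile had really been used, the trial might have been planned with far less power than it claims, or the reported 22 might have no derivation at all. The absence of a stated power for the adopted 30 per group appears to leave that doubt open.

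**Working it through.** **Inputs**, all from section III (1) 4): alpha 0.05 two-sided (quantile 1.96), beta 0.1, difference 6.87, standard deviation 6.85, 15% loss. The last term of the formula carries no subscript in the text available; I take it as the alpha quantile.

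**Formula:** n per group = 2 × [(u_alpha + u_beta) / (delta/sigma)]² + u²/4.

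Standardised difference: 6.87/6.85 = 1.0029. Last term: 1.96²/4 = 0.960.

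**The plan's own figure, with the quantile that beta = 0.1 requires (1.282; Phi(1.282) = 0.900):**
- 2 × (3.242/1.0029)² = 20.90
- 20.90 + 0.96 = 21.86, so 22 per group
- 22/0.85 = 25.88, so 26 per group
- 2 × 26 = 52 in total

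These are the stated 22, 26 and 52.

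**With the quantile as printed (0.282; Phi(0.282) = 0.611):**
- 2 × (2.242/1.0029)² = 9.995
- 9.995 + 0.960 = 10.96, so 11 per group
- 11/0.85 = 12.94, so 13 per group
- 2 × 13 = 26 in total

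None of these results appears in the plan.

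**Does another reading rescue 0.282?** No. Dropping the last term gives 10 per group. A one-sided alpha quantile of 1.645 gives 9. Taking the last term as the beta quantile gives 9.995 + 0.282²/4 = 10.01, so 11. By contrast, 1.282 gives 22 under either reading of the last term (with the beta quantile there, 20.90 + 1.282²/4 = 21.31).

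**Power on the plan's difference and standard deviation** (two-sided t-test at 0.05, noncentral t):

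| Analysed per group | Exact power |
|---|---|
| 11 | 61.0% |
| 22 | 90.1% |
| 25 (30 less 15% = 25.5, rounded down) | 93.5% |
| 26 | 94.4% |
| 30 | 96.9% |

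**The case for a change.** The strongest case for acting is that the printed input and the printed result contradict each other, that the section is the sole basis for the trial's size, and that one digit plus one sentence on power would settle the matter at no cost. The analysis section names a per-protocol analysis, so the number who complete matters, and a stated power of about 93% at 25 analysed per group would be informative.

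The contradiction stands: 0.282 is not the quantile for beta of 0.1, and no reading that keeps it reaches 22. The consequence does not. The quantile is not a separate design choice, because beta fixes it, and beta is stated correctly. Reading the plan as a 61% power calculation lets one misprinted intermediate value override the explicit beta and three results that agree with it.

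The missing power for 30 per group is not an error either. The plan derives a minimum of 26 and rounds up, so on the same assumptions power must exceed the target, and any reader can compute it as above. The text was also converted from PDF, and the subscripts in this sentence are damaged, so the sponsor's document may not contain the wrong digit at all. That cannot be settled from the text available.

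**Conclusion.** This is a clerical slip with no consequence. One intermediate value, 0.282, should read 1.282 to match the stated beta of 0.1. The stated alpha, beta, difference and standard deviation give 22 per group, 26 after 15% loss and 52 in total, exactly as reported. The trial is neither mis-sized nor planned at 61% power. With 30 per group adopted, power is 96.9% if all are analysed and 93.5% at 25 per group, both above the 90% target.

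These powers rest on the plan's own difference of 6.87 and standard deviation of 6.85, which the document attributes to a literature review and which cannot be checked from it. They also assume that loss does not exceed 15%. Correcting the digit would tidy the text, but it would change no enrolment figure, analysis or conclusion, so no change to the plan is called for.

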### **(2) Research Tool**

① General Data questionnaire; ② Caregiver Burden Scale (Caregiver Burden Inventory, CBI); ③ Social Support Rating Scale (Social Support Rating Scale, SSRS); ④ Dementified Caregiver Knowledge Assessment Scale (Dementia Caring Knowledge Scale, DCKS).

### **(3) Data Processing and Statistical Analysis**

Statistical data was analyzed using SPSS 25.0 software. Quantitative data were represented by normal distribution ( $\pm s$ ), non-normal by M (QR); qualitative data by n (%). Quantitative data is designed to compare two independent samples. If sample data follows normality, independent sample t-test is used, otherwise Mann Whitney U test is used; for comparison before and after intervention; if the difference follows normal distribution, paired t-test is used, otherwise Wilcoxon rank sum test is used. To compare qualitative data between different groups, use  $\chi^2$  test or Fisher's exact test; compare rank data between different groups. Subject analysis (Per-protocol Subjects Analysis, PP).

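### Caregiver burden is compared between groups only with an unadjusted test; ANCOVA on baseline CBI would give a more precise estimate at almost no cost if allocation is random

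*Combined protocol and SAP*

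**What the plan says.** The sample size section (III, (1), 4)) names the main outcome: "with the caregiver care burden as the main outcome measure of this study". The CBI is the only burden scale listed under (2) Research Tool. The same sample size section sizes the study at 1:1 by a "difference test of two sample means comparison", with a "two-sided test" at 0.05, a difference of 33.91 − 27.04 = 6.87 and an SD of 6.85, described only as the "overall standard deviation of the intervention".

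Section III (3), Data Processing and Statistical Analysis, is the whole analysis plan. Between groups it provides: "If sample data follows normality, independent sample t-test is used, otherwise Mann Whitney U test is used". Within groups it provides: "for comparison before and after intervention; if the difference follows normal distribution, paired t-test is used", with a Wilcoxon test otherwise. The within-group tests do not compare the arms. No covariate, regression, ANCOVA or mixed model appears anywhere.

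The document gives a 1:1 ratio and convenience sampling, but no method of allocation. It does not state whether the between-group test is applied to follow-up or to change scores.

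**The concern.** A before-after comparison needs a pre-intervention score, so the plan implies that baseline CBI will be available for each participant. A caregiver's burden before the intervention probably predicts the burden afterwards. An unadjusted comparison leaves that predictable variation in the error term, whereas ANCOVA removes it. With about 25 completers per arm, the width of the confidence interval for the burden difference matters to anyone judging whether the programme is worth adopting, and the plan gives up width that it could recover from data it already intends to hold.

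There is a smaller gain in clarity. Follow-up and change-score t-tests can give different answers on the same data. With baseline as covariate, the estimated group effect is the same whichever of the two is the dependent variable.

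**Working it through.** **Inputs from the sample size section.** Difference 6.87; SD 6.85; two-sided 0.05; power 90%; 15% dropout; 30 per group.

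**Assumptions.** 6.85 is the SD of a single score, equal at both times. The baseline to follow-up correlation r is 0.3, 0.5 or 0.7; the documents give no value. Completers per arm: 30 × 0.85 = 25.5, taken as 25.

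**The plan's own figure.** 2[(1.96 + 1.282)/(6.87/6.85)]² + 1.96²/4 = 20.90 + 0.96 = 21.86, so 22 per group. Then 22/0.85 = 25.9, so 26. Both stated figures reproduce. They need the quantile 1.282; the printed 0.282 would give 9.99 + 0.96 = 10.96, so 11. It looks like a slip and does not affect the stated size.

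**Planned test, 25 per arm.** SE = 6.85 × √(2/25) = 1.937. Half-width = 2.011 × 1.937 = 3.90 points (48 df). Power from the noncentral t = 93.5%.

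**ANCOVA, 25 per arm.** The residual variance is multiplied by 1 − r². With 47 df (t = 2.012) and the slope treated as known, the half-width is 2.012 × 1.937 × √(1 − r²). The slope must be estimated, which multiplies the SE by √(1 + D²/(SS × 2/25)), where D is the baseline difference between arms and SS the pooled within-arm sum of squares of baseline. Under random allocation this factor is about 1.005 in a typical (median) trial and about √(1 + 1/46) = 1.011 on average.

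| r | 1 − r² | Half-width, slope known | with factor 1.005 | with factor 1.011 | Power |
|---|---|---|---|---|---|
| 0.3 | 0.91 | 3.72 | 3.74 | 3.76 | about 95% |
| 0.5 | 0.75 | 3.38 | 3.39 | 3.41 | about 98% |
| 0.7 | 0.51 | 2.78 | 2.80 | 2.81 | 99.8% |

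Simulated power with the slope estimated (40,000 replicates) was 95.0%, 97.6% and 99.8%.

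**Cost if baseline predicts nothing (r = 0).** With the slope estimated, power at 30 per group goes from 96.9% to about 96.6%, and at 22 per group from 90.1% to about 89.4%.

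**Chance imbalance.** A baseline difference D shifts the follow-up contrast by rD on average. Over random allocations that shift has variance r² × 2σ²/n, which is exactly the part that the factor 1 − r² removes. It is already counted in the half-widths above.

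**If groups are not randomised.** Take, for illustration, a pre-existing difference of 0.3 SD = 0.3 × 6.85 = 2.06 points.
- If it fully persists, follow-up scores are biased by 2.06 points, ANCOVA by (1 − r) × 2.06 = 1.44, 1.03 or 0.62, and change scores by 0.
- If it does not persist, follow-up scores are unbiased and ANCOVA is off by r × 2.06 = 0.62, 1.03 or 1.44 in the other direction.

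**The case against.** The strongest reply is that nothing here is an error. The two-sample t-test matches the method used for sizing, is valid under random allocation, and exceeds its 90% target on the plan's inputs. The whole gain depends on a correlation that the documents do not give, and at 0.3 it is worth about 0.16 points of half-width (3.90 − 3.74). All of that stands, and it confines the point to precision.

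Three stronger readings are tempting, and the documents do not support them.

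- A reader might infer that the unnamed score leaves the trial underpowered. If 6.85 were the SD of change, a follow-up comparison at r = 0.7 would have only 77% power. But nothing in the text says that 6.85 is an SD of change. The sizing subtracts two score levels, and the analysis section speaks of a difference only for the before-after test. Follow-up scores are the natural reading; the missing statement is mostly a lack of detail.
- A reader might count exposure to chance baseline imbalance as a second harm. Under randomisation it is the same variance as the precision loss, and the t-test's standard error already allows for it.
- A reader might expect ANCOVA to protect against confounding if groups were not randomised. The illustration above shows that it can leave bias, or introduce some where the unadjusted test had none.

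It is also fair that baseline collection is inferred from the before-after wording, since no assessment schedule is given, and that a covariate model needs a stated answer for non-normal data.

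**Conclusion.** The point holds as a worthwhile improvement in efficiency, not as a flaw that invalidates the plan. The cost is one degree of freedom plus roughly 0.5% to 1% on the standard error, against a half-width reduction of about 4% at r = 0.3 (3.74/3.90), 13% at 0.5 (3.39/3.90) and 28% at 0.7 (2.80/3.90).

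This rests on 6.85 being the raw-score SD, equal SDs at both times, 25 completers per arm, baseline CBI actually being measured, and the assumed range of r. Above all it rests on random allocation, which the document neither describes nor rules out.

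**What to change.** In section III (3):

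- Make the primary analysis an ANCOVA of post-intervention CBI on group with baseline CBI as covariate, and report the adjusted mean difference with its 95% CI.
- Let this replace both the t-test and the Mann-Whitney branch for the group comparison. Check the residuals and, if they are clearly non-normal, add a rank-based or bootstrap version as a sensitivity analysis.
- Use the same model for SSRS and DCKS, each with its own baseline score.
- State how groups are allocated. If they are not randomised, show the change-score result beside the ANCOVA and say that baseline adjustment may not remove the bias.

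This is a change of wording. The SPSS 25.0 already named in the plan fits the model. No extra participants are needed, and no extra measurement provided baseline scores are taken, as the before-after comparison implies; the plan should state that they are.

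### The non-normal fallback for the paired before-after comparison is named as the Wilcoxon rank sum test, which is for independent samples; it should be the signed-rank test

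*Combined protocol and SAP*

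**What the plan says.** Section III (3), Data Processing and Statistical Analysis, sets two rules for quantitative outcomes.

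- Two independent samples: "If sample data follows normality, independent sample t-test is used, otherwise Mann Whitney U test is used".
- Paired data, introduced by "for comparison before and after intervention": "if the difference follows normal distribution, paired t-test is used, otherwise Wilcoxon rank sum test is used".

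The signed-rank test is not named anywhere in the document. The quantitative outcomes are the three scales in Research Tool: caregiver burden (CBI), social support (SSRS) and dementia care knowledge (DCKS). Caregiver burden is the main outcome according to Sample size estimation, which sizes the trial on a between-group method, the "difference test of two sample means comparison".

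**The concern.** The before-after rule is a paired rule in every respect but its last term. It checks normality of the within-caregiver difference and, if that holds, uses a paired t-test. The matching rank procedure is the Wilcoxon signed-rank test, which works on the same differences. The rank sum test discards the pairing: it pools all scores, ranks them together, and computes its null variance as if the before and after scores came from separate people.

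When a caregiver's two scores are positively correlated, that variance is too large. The p-value then loses its nominal 5% level, and the test can miss a modest change within an arm. At stake are the within-arm before-after results on the three scales whenever the normality check fails.

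**Working it through.** **1. The two rules side by side**

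| Comparison | If normal | If not normal | Fallback designed for |
|---|---|---|---|
| Two independent samples | Independent t-test | Mann-Whitney U | Independent samples |
| Before vs after, same caregiver | Paired t-test | Wilcoxon rank sum | Independent samples (equivalent to Mann-Whitney U) |

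One procedure, under two names, is assigned to two different designs. This follows from the definitions and needs no simulation.

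**2. The plan's own figures (for context)**

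Sample size estimation gives δ = 33.91 − 27.04 = 6.87, σ = 6.85, two-sided α = 0.05, β = 0.1.

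- n = 2[(1.96 + 1.282)/(6.87/6.85)]² + 1.96²/4 = 20.90 + 0.96 = 21.86, so 22 per group, as stated.
- 22/0.85 = 25.9, so 26 with 15% dropout, as stated. The plan enrols 30 per group.
- The β quantile is printed as 0.282; the stated 22 is reproduced with 1.282.
- Standardised between-group effect: 6.87/6.85 = 1.003 SD.

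The choice of paired fallback enters none of this.

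**3. Direction of the error**

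If before and after scores share one distribution and have rank correlation ρ, then in large samples the true null variance of the rank sum statistic is (1 − ρ) times the variance the test assumes. The actual two-sided error at nominal 5% is therefore about 2Φ(−1.96/√(1 − ρ)):

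- ρ = 0.3: 2Φ(−2.34) = 1.9%
- ρ = 0.5: 2Φ(−2.77) = 0.6%
- ρ = 0.7: 2Φ(−3.58) = 0.03%

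**4. Size when the fallback is triggered**

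The documents give no before-after correlation, score distribution, normality test or expected within-arm change. Assumed here: gamma(2) scores, Shapiro-Wilk at 5%, a 0.5 SD change, and 25 or 30 pairs per arm. Correlation was built by a shared component or a Gaussian copula (for the copula, the figure is the latent correlation), with 3,000 to 6,000 data sets per setting. Monte Carlo error of these conditional figures is about 1 to 2 points.

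| Correlation | Type I error, rank sum | Type I error, signed-rank | Power, rank sum | Power, signed-rank |
|---|---|---|---|---|
| 0.3 | 1.6-2.2% | 5.0-6.4% | 54-67% | 62-74% |
| 0.5 | 0.5-1.2% | 5.4-6.4% | 55-67% | 76-86% |
| 0.7 | 0-0.2% | 4.4-6.1% | 59-71% | 91-97% |

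A separate simulation applied both tests to every data set, with no normality check (skewed shared component plus normal errors, 30 pairs, 10,000 data sets). It shows the same pattern. At correlations 0.3, 0.5 and 0.7, rank sum type I error was 2.8%, 1.3% and 0.3% against 5.0-5.2% for signed-rank. Power was 47%, 50% and 59% against 59%, 74% and 92%.

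**5. Size over the whole rule**

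The fallback is triggered in only some data sets: 20-26% of the gamma data sets at correlation 0.3, 21-37% at 0.5, 23-58% at 0.7, and about 5% of normal ones. Power of the rule as written against the corrected rule, 0.5 SD change:

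| Correlation | Shared component, n = 25 | Copula, n = 25 | Shared component, n = 30 | Copula, n = 30 | Loss (points) |
|---|---|---|---|---|---|
| 0.3 | .571 / .597 | .544 / .556 | .658 / .676 | .647 / .658 | 1-3 |
| 0.5 | .666 / .738 | .657 / .703 | .750 / .822 | .729 / .768 | 4-7 |
| 0.7 | .750 / .927 | .805 / .879 | .808 / .964 | .861 / .927 | 7-18 |

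For normal data at n = 25 the figures are .649 / .665 (correlation 0.5) and .842 / .871 (0.7), a loss of 2 to 3 points. Whole-rule type I error at correlation 0.5 is 3.6-4.0% as written and 5.1-5.3% corrected.

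**6. Where it stops mattering**

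- For a 1.0 SD change (shared component, n = 25, fallback triggered), power is .984 / .987, .990 / .997 and .994 / 1.000 at correlations 0.3, 0.5 and 0.7: a loss of under 1 point.
- At correlation 0 (same setting), type I error is .041 / .045 and power at 0.5 SD is .525 / .452. There is no loss; the rank sum test is ahead.

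**The case against.** The strongest reply is that this is a slip of terminology. The sentence speaks of the difference and names the paired t-test, so a paired comparison is clearly intended. The plan also uses one name for the independent-samples fallback and another for the paired one, which suggests two distinct tests were meant. The rest of the paragraph reads like rough translation. Nothing in the document shows that a rank sum test was or would be run on paired scores.

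Nor does the point reach the main comparison. The trial is sized on a between-group contrast, and in a two-arm study a within-arm change is supporting evidence only. The error is conservative, the largest power gaps occur only when the fallback is triggered and at the highest assumed correlation, and every simulation input beyond the plan's sample size is an assumption.

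Most of this stands as a limit on the weight of the point. A naming slip is quite possible, the main comparison is unaffected, and the whole-rule figures are the ones to judge by. None of it makes the wording correct. The plan is the only statement of the rule, no other text corrects it, and an analyst following it literally would run a test that does not fit the design.

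**Conclusion.** The concern holds. As written, the plan names an independent-samples test for a paired comparison. This should be fixed, but it does not threaten the main result.

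The effect is confined to the non-normal branch of the within-arm before-after tests. With positive correlation it costs power rather than creating false positives: for a 0.5 SD change, 1 to 18 points over the whole rule across correlations 0.3 to 0.7 with skewed scores, and 2 to 3 points with normal scores at correlations 0.5 to 0.7. These sizes depend on the assumed correlation, score shape, normality check and change. The mismatch between test and design depends on none of them.

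**What to change.** In Data Processing and Statistical Analysis, change the fallback for the before-after comparison from the Wilcoxon rank sum test to the Wilcoxon signed-rank test. Leave Mann-Whitney U in place for the two independent samples.

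If the analysis has already been done, check the output to see which test was run, and rerun the affected comparisons if it was the rank sum test.

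The cost is one term in the plan and no new data. A rerun would cover at most six tests (three scales, two arms), assuming before-after tests in both arms on every scale at one post-intervention time point; the plan does not specify these.
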